10.1.7 Compliance with Law, Audit, and Debarment

By signing this protocol, the investigator agrees to conduct the study in an efficient and diligent manner and in conformance with this protocol; generally accepted standards of GCP (eg, International Council on Harmonisation of Technical Requirements for Registration of Pharmaceuticals for Human Use GCP: Consolidated Guideline and other generally accepted standards of GCP); and all applicable federal, state and local laws, rules and regulations relating to the conduct of the clinical study.

The Code of Conduct, a collection of goals and considerations that govern the ethical and scientific conduct of clinical investigations sponsored by MSD, is provided in this appendix under the Code of Conduct for Clinical Trials.

This study, sponsored by Butantan, will be conducted in a manner consistent with the MSD Code of Conduct for Clinical Trials (Section 10.1.1).

Section III.A. (Regulatory Authority and Ethics Committee Review) of the Code of Conduct is adapted for this study to clarify that it is the Sponsor's responsibility to submit the protocol and protocol amendments to the regulatory authorities, as follows:

All protocols and protocol amendments will be submitted by the Sponsor for regulatory authority acceptance/authorization prior to implementation of the trial or amendment, in compliance with local and/or national regulations.

The protocol, protocol amendment(s), informed consent form, investigator's brochure, and other relevant trial documents must be reviewed and approved by an IRB/IEC before being implemented at each site, in compliance with local and/or national regulations.

Changes to the protocol that are required urgently to eliminate an immediate hazard and to protect participant safety may be enacted in anticipation of ethics committee approval. The Sponsor will inform regulatory authorities of such new measures to protect participant safety, in compliance with local and/or national regulations.

Section IV.B. (Clinical Research Funding) of the Code of Conduct is adapted for this study to accurately identify Butantan as the trial Sponsor, as follows:

Informed consent forms will disclose that the trial is sponsored by Butantan, and that the investigator or sponsoring institution is being paid or provided a grant for performing the trial. However, the local ethics committee may wish to alter the wording of the disclosure statement to be consistent with financial practices at that institution. As noted above, all publications resulting from this trial will indicate MSD as a source of funding.

The investigator agrees not to seek reimbursement from participants, their insurance providers, or from government programs for procedures included as part of the study reimbursed to the investigator by MSD.

The investigator will promptly inform MSD of any regulatory authority inspection conducted for this study.

The investigator agrees to provide MSD with relevant information from inspection observations/findings to allow the Sponsor and/or MSD to assist in responding to any citations resulting from regulatory authority inspection and will provide MSD with a copy of the proposed response for consultation before submission to the regulatory authority.

Persons debarred from conducting or working on clinical studies by any court or regulatory authority will not be allowed to conduct or work on MSD's studies. The investigator will immediately disclose in writing to MSD if any person who is involved in conducting the study is debarred or if any proceeding for debarment is pending or, to the best of the investigator's knowledge, threatened.

10.1.8 Data Quality Assurance

All participant data relating to the study will be recorded on printed or electronic CRF unless transmitted to MSD or designee electronically (eg, laboratory data). The investigator or qualified designee is responsible for verifying that data entries are accurate and correct by physically or electronically signing the CRF.

Detailed information regarding Data Management procedures for this protocol will be provided separately.

The investigator must maintain accurate documentation (source data) that supports the information entered in the CRF.

The investigator must permit study-related monitoring, audits, IRB/IEC review, and regulatory agency inspections and provide direct access to source data documents.

Study documentation will be promptly and fully disclosed to MSD by the investigator upon request and also shall be made available at the study site upon request for inspection, copying, review, and audit at reasonable times by representatives of MSD or any regulatory authorities. The investigator agrees to promptly take any reasonable steps that are requested by MSD or any regulatory authorities as a result of an audit or inspection to cure deficiencies in the study documentation and worksheets/CRFs.

MSD or designee is responsible for the data management of this study including quality checking of the data.

Study monitors will perform ongoing source data review and verification to confirm that data entered into the CRF by authorized site personnel are accurate, complete, and verifiable from source documents; that the safety and rights of participants are being protected; and that the

study is being conducted in accordance with the currently approved protocol and any other study agreements, ICH GCP, and all applicable regulatory requirements.

Records and documents, including participants' documented informed consent, pertaining to the conduct of this study must be retained by the investigator for 15 years after study completion unless local regulations or institutional policies require a longer retention period. No records may be destroyed during the retention period without the written approval of MSD. No records may be transferred to another location or party without written notification to MSD.

10.1.9 Source Documents

Source documents provide evidence for the existence of the participant and substantiate the integrity of the data collected. The investigator/institution should maintain adequate and accurate source documents and study records that include all pertinent observations on each of the site's participants. Source documents and data should be attributable, legible, contemporaneous, original, accurate, and complete. Changes to source data should be traceable, should not obscure the original entry, and should be explained if necessary (eg, via an audit trail). Source documents are filed at the investigator's site.

Data reported on the CRF or entered in the eCRF that are transcribed from source documents must be consistent with the source documents or the discrepancies must be explained. The investigator/institution may need to request previous medical records or transfer records, depending on the study. Also, current medical records must be available.

10.1.10 Study and Site Closure

MSD in collaboration with the Sponsor or its designee may stop the study or study site participation in the study for medical, safety, regulatory, administrative, or other reasons consistent with applicable laws, regulations, and GCP.

In the event MSD in collaboration with the Sponsor prematurely terminates a particular study site, MSD or designee will promptly notify that study site's IRB/IEC as specified by applicable regulatory requirement(s).

10.2 Appendix 2: Clinical Laboratory Tests

Safety laboratory assessments (ie, blood chemistry, hematology, and urinalysis) are not planned for this study.

10.3 Appendix 3: Adverse Events: Definitions and Procedures for Recording, Evaluating, Follow-up, and Reporting

10.3.1 Definitions of Medication Error, Misuse, and Abuse

Medication Error

This is an unintended failure in the drug treatment process that leads to or has the potential to lead to harm to the participant.

Misuse

This refers to situations where the medicinal product is intentionally and inappropriately used not in accordance with the terms of the product information.

Abuse

This corresponds to the persistent or sporadic, intentional excessive use of a medicinal product for a perceived psychological or physiological reward or desired non-therapeutic effect.

10.3.2 Definition of AE

AE definition

- An AE is any untoward medical occurrence in a clinical study participant, temporally associated with the use of study intervention, whether or not considered related to the study intervention.
- NOTE: An AE can therefore be any unfavorable and unintended sign (including an abnormal laboratory finding), symptom, or disease (new or exacerbated) temporally associated with the use of a study intervention.
- NOTE: For purposes of AE definition, study intervention (also referred to as Sponsor or MSD's product) includes any pharmaceutical product, biological product, vaccine, diagnostic agent, medical device, combination product, or protocol-specified procedure whether investigational or marketed (including placebo, active comparator product, or run-in intervention), manufactured by, licensed by, provided by, or distributed by the Sponsor or MSD for human use in this study.

Events meeting the AE definition

- Any abnormal laboratory test results (hematology, clinical chemistry, or urinalysis) or other safety assessments (eg, ECG, radiological scans, vital signs measurements), including those that worsen from baseline, considered clinically significant in the medical and scientific judgment of the investigator.

- Exacerbation of a chronic or intermittent pre-existing condition including either an increase in frequency and/or intensity of the condition.
- New conditions detected or diagnosed after study intervention administration even though it may have been present before the start of the study.
- Signs, symptoms, or the clinical sequelae of a suspected drug-drug interaction.
- Signs, symptoms, or the clinical sequelae of a suspected overdose of either study intervention or a concomitant medication.
- For all reports of overdose (whether accidental or intentional) with an associated AE, the AE term should reflect the clinical symptoms or abnormal test result. An overdose without any associated clinical symptoms or abnormal laboratory results is reported using the terminology “accidental or intentional overdose without adverse effect.”
- Any new cancer or progression of existing cancer.

Events NOT meeting the AE definition

- Medical or surgical procedure (eg, endoscopy, appendectomy): the condition that leads to the procedure is the AE.
- Situations in which an untoward medical occurrence did not occur (social and/or convenience admission to a hospital).
- Anticipated day-to-day fluctuations of pre-existing disease(s) or condition(s) present or detected at the start of the study that do not worsen.
- Surgery planned prior to informed consent to treat a pre-existing condition that has not worsened.
- Refer to Section 8.4.6 for protocol-specific exceptions.

Definition of Solicited and Unsolicited AE

- Solicited AEs are predefined local (at the injection site) and systemic events for which the participant is specifically questioned, and which are noted by the participant in the eVRC.
- An unsolicited AE is an AE that was not solicited using an eVRC and that is communicated by a participant who has provided documented informed consent. Unsolicited AEs include serious and nonserious AEs and may be reported via the eVRC or via other methods.

Definition of MAAE

- AEs in which medical attention is received during an unscheduled, non-routine outpatient visit, such as an ER visit, office visit, or an urgent care visit with any medical personnel for any reason. Routine visits are not considered MAAEs. Examples of routine visits include: physical examination, wellness visits, or vaccinations.
- Determination of MAAEs is the responsibility of the investigator or a qualified designee. Once identified, MAAEs should be reported to MSD per the timeline for reporting AEs/SAEs.

NOTE: For this study a febrile event reported during an acute visit (see Section 8.3.6) is considered an MAAE.

10.3.3 Definition of SAE

If an event is not an AE per definition above, then it cannot be an SAE even if serious conditions are met.

An SAE is defined as any untoward medical occurrence that, at any dose:

a. **Results in death**

b. **Is life-threatening**

- The term “life-threatening” in the definition of “serious” refers to an event in which the participant was at risk of death at the time of the event. It does not refer to an event, which hypothetically might have caused death, if it were more severe.

c. **Requires inpatient hospitalization or prolongation of existing hospitalization**

- Hospitalization is defined as an inpatient admission, regardless of length of stay, even if the hospitalization is a precautionary measure for continued observation. (Note: Hospitalization for an elective procedure to treat a pre-existing condition that has not worsened is not an SAE.) A pre-existing condition is a clinical condition that is diagnosed prior to the use of Sponsor or MSD’s product and is documented in the participant’s medical history.

d. **Results in persistent or significant disability/incapacity**

- The term disability means a substantial disruption of a person’s ability to conduct normal life functions.
- This definition is not intended to include experiences of relatively minor medical significance such as uncomplicated headache, nausea, vomiting, diarrhea, influenza, and accidental trauma (eg, sprained ankle) that may interfere with or prevent everyday life functions but do not constitute a substantial disruption.

e. Is a congenital anomaly/birth defect

- In offspring of participant taking the product regardless of time to diagnosis.

f. Other important medical events

- Medical or scientific judgment should be exercised in deciding whether SAE reporting is appropriate in other situations such as important medical events that may not be immediately life-threatening or result in death or hospitalization but may jeopardize the participant or may require medical or surgical intervention to prevent 1 of the other outcomes listed in the above definition. These events should usually be considered serious.

Examples of such events include invasive or malignant cancers, intensive treatment in an emergency room or at home for allergic bronchospasm, blood dyscrasias or convulsions that do not result in hospitalization, or development of drug dependency or drug abuse.

10.3.4 Additional Events Reported

Additional events that require reporting

In addition to the above criteria, AEs meeting either of the below criteria, although not serious per ICH definition, are reportable to MSD.

- Is a cancer
- Is associated with an overdose

10.3.5 Recording AE and SAE

AE and SAE recording

- When an AE/SAE occurs, it is the responsibility of the investigator to review all documentation (eg, hospital progress notes, laboratory, and diagnostics reports) related to the event.
- The investigator will record all relevant AE/SAE information on the AE CRFs/worksheets at each examination.
- It is not acceptable for the investigator to send photocopies of the participant's medical records to MSD in lieu of completion of the AE CRF page.
- There may be instances when copies of medical records for certain cases are requested by MSD. In this case, all participant identifiers, with the exception of the participant number, will be blinded on the copies of the medical records before submission to MSD.

- The investigator will attempt to establish a diagnosis of the event based on signs, symptoms, and/or other clinical information. In such cases, the diagnosis (not the individual signs/symptoms) will be documented as the AE/SAE.

Assessment of intensity

- An event is defined as “serious” when it meets at least 1 of the predefined outcomes as described in the definition of an SAE, not when it is rated as severe.
- The investigator will make an assessment of overall intensity grade for each AE and SAE (and other reportable event) reported during the study. An overall intensity grade will be assigned to injection-site AEs, specific systemic AEs, other systemic AEs, and vital sign (temperature) AEs as shown in the following tables. The overall intensity grading scales used in this study are adapted from the “FDA Guidance for Industry: Toxicity Grading Scale for Healthy Adult and Adolescent Volunteers Enrolled in Preventive Vaccine Clinical Trials, September 2007” [Food and Drug Administration 2007].

Injection-Site AE Overall Intensity Grading Scale

Injection-Site Reaction to Study Vaccine ^a	Mild (Grade 1)	Moderate (Grade 2)	Severe (Grade 3)	Potentially Life-Threatening (Grade 4)
Injection-site AEs occurring Days 1 through 5 following receipt of study vaccine				
Pain/Tenderness	Does not interfere with activity	Repeated use of non-narcotic pain reliever >24 hours or interferes with activity	Any use of narcotic pain reliever or prevents daily activity	ER visit or hospitalization
Erythema/Redness	≤5 cm (size measured as A or B)	5.1 to 10 cm (size measured as C or D)	>10 cm (size measured as E→)	Necrosis or exfoliative dermatitis or results in ER visit or hospitalization
Swelling	≤5 cm (size measured as A or B)	5.1 to 10 cm (size measured as C or D)	>10 cm (size measured as E→)	Necrosis or ER visit or hospitalization
Other	Does not interfere with activity	Repeated use of non-narcotic pain reliever >24 hours or interferes with activity	Any use of narcotic pain reliever or prevents daily activity	ER visit or hospitalization
Any injection-site reaction that begins ≥6 days after receipt of study vaccine				
Pain/Tenderness Erythema/Redness Swelling Other	Does not interfere with activity	Repeated use of non-narcotic pain reliever >24 hours or interferes with activity	Any use of narcotic pain reliever or prevents daily activity	ER visit or hospitalization

Injection-Site Reaction to Study Vaccine ^a	Mild (Grade 1)	Moderate (Grade 2)	Severe (Grade 3)	Potentially Life-Threatening (Grade 4)
Injection-site AEs occurring Days 1 through 5 following receipt of study vaccine				
AE=adverse event; ER=emergency room; eVRC=electronic Vaccination Report Card The overall intensity grading scales used in this study are adapted from the “FDA Guidance for Industry: Toxicity Grading Scale for Healthy Adult and Adolescent Volunteers Enrolled in Preventive Vaccine Clinical Trials, September 2007” [Food and Drug Administration 2007].				

Specific Systemic AE Overall Intensity Grading Scale

Systemic (General)	Mild (Grade 1)	Moderate (Grade 2)	Severe (Grade 3)	Potentially Life-Threatening (Grade 4)
Headache	No interference with activity	Repeated use of non-narcotic pain reliever >24 hours or some interference with activity	Significant; any use of narcotic pain reliever or prevents daily activity	ER visit or hospitalization
Fatigue/tiredness	No interference with activity	Some interference with activity	Significant; prevents daily activity	ER visit or hospitalization
Muscle pain/myalgia	No interference with activity	Some interference with activity	Significant; prevents daily activity	ER visit or hospitalization
Joint pain/arthritis	No interference with activity	Some interference with activity	Significant; prevents daily activity	ER visit or hospitalization
Rash	No interference with activity	Some interference with activity	Significant; prevents daily activity	ER visit or hospitalization

ER=emergency room

The overall intensity grading scales used in this study are adapted from the “FDA Guidance for Industry: Toxicity Grading Scale for Healthy Adult and Adolescent Volunteers Enrolled in Preventive Vaccine Clinical Trials, September 2007” [Food and Drug Administration 2007].

Other Systemic AE Overall Intensity Grading Scale

Systemic Illness ^a	Mild (Grade 1)	Moderate (Grade 2)	Severe (Grade 3)	Potentially Life-Threatening (Grade 4) ^b
Illness or clinical AE (as defined according to applicable regulations)	No interference with activity	Some interference with activity not requiring medical intervention	Prevents daily activity and required medical intervention	ER visit or hospitalization
AE=adverse event; ER=emergency room; eVRC=electronic Vaccination Report Card; SAE=serious adverse event The overall intensity grading scales used in this study are adapted from the "FDA Guidance for Industry: Toxicity Grading Scale for Healthy Adult and Adolescent Volunteers Enrolled in Preventive Vaccine Clinical Trials, September 2007" [Food and Drug Administration 2007].				
^a Based upon information provided by the participant on the eVRC and verbally during the eVRC review during the primary safety follow-up period. For SAEs reported beyond the primary safety follow-up period, grading will be based upon the initial report and/or follow-up of the event.				
^b AEs resulting in death will be assessed as Grade 4.				

Vital Sign (Temperature) Overall Intensity Grading Scale

Vital Signs ^a	Mild (Grade 1)	Moderate (Grade 2)	Severe (Grade 3)	Potentially Life-Threatening (Grade 4)
Fever (°C) ^b (°F) ^b	38.0 to 38.4 100.4 to 101.1	38.5 to 38.9 101.2 to 102.0	39.0 to 40.0 102.1 to 104.0	>40.0 >104.0
The overall intensity grading scales used in this study are adapted from the "FDA Guidance for Industry: Toxicity Grading Scale for Healthy Adult and Adolescent Volunteers Enrolled in Preventive Vaccine Clinical Trials, September 2007" [Food and Drug Administration 2007].				
^a Participant should be at rest for all vital sign requirements.				
^b Oral temperature; no recent hot or cold beverages or smoking.				

Assessment of causality

- Did the Sponsor or MSD's product cause the AE?
- The determination of the likelihood that the Sponsor or MSD's product caused the AE will be provided by an investigator who is a qualified physician. The investigator's signed/dated initials on the source document or worksheet that supports the causality noted on the AE form, ensures that a medically qualified assessment of causality was done. This initialled document must be retained for the required regulatory time frame. The criteria below are intended as reference guidelines to assist the investigator in assessing the likelihood of a relationship between the test product and the AE based upon the available information.
- **The following components are to be used to assess the relationship between the Sponsor or MSD's product and the AE;** the greater the correlation with the

components and their respective elements (in number and/or intensity), the more likely the Sponsor or MSD's product caused the AE:

- **Exposure:** Is there evidence that the participant was actually exposed to the Sponsor or MSD's product such as: reliable history, acceptable compliance assessment (diary, etc.), seroconversion or identification of vaccine virus in bodily specimen?
- **Time Course:** Did the AE follow in a reasonable temporal sequence from administration of the Sponsor or MSD's product? Is the time of onset of the AE compatible with a vaccine-induced effect?
- **Likely Cause:** Is the AE not reasonably explained by another etiology such as underlying disease, other drug(s)/vaccine(s), or other host or environmental factors?
- **Rechallenge:** Was the participant re-exposed to the Sponsor or MSD's product in the study?
 - If yes, did the AE recur or worsen?
 - If yes, this is a positive rechallenge.
 - If no, this is a negative rechallenge.

(Note: This criterion is not applicable if: (1) the initial AE resulted in death or permanent disability, or (2) the study is a single-dose vaccine study; or (3) Sponsor or MSD's product(s) is/are used only 1 time.)

NOTE: IF A RECHALLENGE IS PLANNED FOR AN AE THAT WAS SERIOUS AND MAY HAVE BEEN CAUSED BY THE SPONSOR OR MSD'S PRODUCT, OR IF RE-EXPOSURE TO THE SPONSOR OR MSD'S PRODUCT POSES ADDITIONAL POTENTIAL SIGNIFICANT RISK TO THE PARTICIPANT THEN THE RECHALLENGE MUST BE APPROVED IN ADVANCE BY THE MSD CLINICAL DIRECTOR, AND IF REQUIRED, THE IRB/IEC.

- **Consistency with study intervention profile:** Is the clinical/pathological presentation of the AE consistent with previous knowledge regarding the Sponsor or MSD's product or drug class pharmacology or toxicology?
- The assessment of relationship will be reported on the CRFs/worksheets by an investigator who is a qualified physician according to his/her best clinical judgment, including consideration of the above elements.

- Use the following scale of criteria as guidance (not all criteria must be present to be indicative of a Sponsor or MSD's product relationship).
 - Yes, there is a reasonable possibility of Sponsor or MSD's product relationship:
 - There is evidence of exposure to the Sponsor or MSD's product. The temporal sequence of the AE onset relative to the administration of the Sponsor or MSD's product is reasonable. The AE is more likely explained by the Sponsor or MSD's product than by another cause.
 - No, there is not a reasonable possibility of Sponsor or MSD's product relationship:
 - Participant did not receive the Sponsor or MSD's product OR temporal sequence of the AE onset relative to administration of the Sponsor or MSD's product is not reasonable OR the AE is more likely explained by another cause than the Sponsor or MSD's product. (Also entered for a participant with overdose without an associated AE.)
- For each AE/SAE, the investigator must document in the medical notes that he/she has reviewed the AE/SAE and has provided an assessment of causality.
- There may be situations in which an SAE has occurred and the investigator has minimal information to include in the initial report to MSD. However, it is very important that the investigator always make an assessment of causality for every event before the initial transmission of the SAE data to MSD.
- The investigator may change his/her opinion of causality in light of follow-up information and send an SAE follow-up report with the updated causality assessment.
- The causality assessment is 1 of the criteria used when determining regulatory reporting requirements.

Follow-up of AE and SAE

- The investigator is obligated to perform or arrange for the conduct of supplemental measurements and/or evaluations as medically indicated or as requested by MSD to elucidate the nature and/or causality of the AE or SAE as fully as possible. This may include additional laboratory tests or investigations, histopathological examinations, or consultation with other health care professionals.
- New or updated information will be recorded in the CRF.
- The investigator will submit any updated SAE data to MSD within 24 hours of receipt of the information.

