8.3.2 Vital Signs

Vital signs are part of the physical examination at Visit 1 (Day 1) and include axillary body temperature, heart rate, respiratory rate, and seated BP.

BP and heart rate measurements will be assessed after the participant has at least 5 minutes of rest in a quiet setting without distractions, and from a sitting position, with a completely automated device. Manual techniques will be used only if an automated device is not available.

Abnormal vital signs must be confirmed by repeat testing after 15 minutes. Findings related to the vital signs should be documented in the participant source documentation. Any clinically significant abnormality will be recorded on the appropriate eCRF.

Axillary temperatures will be recorded by participants on the eVRC from Day 1 through Day 28 postvaccination. For this study, protocol-specified fever is defined as axillary temperature $\geq 37.8^{\circ}\text{C}$.

For participants with a febrile illness that is assessed as dengue or possible/probable dengue, vital signs will be collected during the acute and convalescent follow-up visits (Section 8.3.6).

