Based on the duration of the participant-reported fever and the serum sample test results, there are 3 possible outcomes, as outlined in [Table 2](#).

Table 2 Evaluation and Outcomes for Febrile Event Assessments

Participant-reported Protocol-specified Fever ^a	Laboratory Result	Outcome
≥2 consecutive days	Positive for RT-PCR and/or NS1 ELISA	Virologically confirmed dengue case, per the protocol-specified definition
1 day or multiple nonconsecutive days	Positive for RT-PCR and/or NS1 ELISA	Dengue case
≥1 day	Negative for RT-PCR and/or NS1 ELISA	Not a dengue case
ELISA=enzyme-linked immunosorbent assay; NS=non-structural protein; RT-PCR=reverse transcription polymerase chain reaction.		
^a Protocol-specified fever is defined as axillary temperature of ≥37.8°C.		

[figure not shown]
[Figure 2](#) outlines possible scenarios for participants who experience protocol-specified fever (axillary temperature of ≥37.8°C) and present at the clinic for an acute visit.

If, based on clinical and/or local laboratory evaluation, the investigator assesses a case as dengue or possible/probable dengue, a convalescent follow-up visit to collect information about the severity and recovery from the febrile illness is to occur 14 to 28 days after the acute visit clinical evaluation. During the convalescent follow-up visit, the investigator will conduct a clinical evaluation. Guidelines for the investigator's clinical assessment of suspected dengue are in Section 10.3.6.

During extended follow-up visits (V5 and V8) and telephone contacts (V6 and V7), all participants will be reminded to schedule an acute visit in the event of at least 2 consecutive days of protocol-specified fever.

Febrile events evaluated by the investigator at an acute visit will be reported as MAAEs. Febrile events evaluated from Day 1 through Day 28 will also be reported as an NSAE. At any time during the study, report febrile events that meet serious criteria as an SAE.

Figure 2 V181-002 Assessment of Febrile Events for Suspected Dengue Disease

ELISA=enzyme-linked immunosorbent assay; MAAE=medically attended adverse event; NS=non-structural protein; RT-PCR=reverse transcription polymerase chain reaction

^a Protocol-specified fever is defined as axillary temperature of $\geq 37.8^{\circ}\text{C}$. All febrile events evaluated at the site (acute visit) will be reported as MAAEs.

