9.4.2 Safety Endpoints

An initial description of safety measures is provided in Section 4.2.1.2. The overall safety and tolerability profile for each vaccine will be assessed by clinical review of all safety data collected. Solicited and unsolicited injection-site and systemic AEs will be summarized overall, and by maximum reported intensity. The primary safety evaluation period for this study will be Day 1 through Day 28 postvaccination.

Primary Safety Endpoints

- Vaccine-related SAEs from Day 1 through Day 28 postvaccination

Secondary Safety Endpoints

- Solicited injection-site AEs of injection-site pain, injection-site erythema, and injection-site swelling from Day 1 through Day 5 postvaccination
- Solicited systemic AEs of rash, headache, fatigue (tiredness), myalgia (muscle pain), and arthralgia (joint pain) from Day 1 through Day 28 postvaccination

Additional Safety Endpoints

- Unsolicited AEs from Day 1 through Day 28 postvaccination
- Elevated temperature ($\geq 37.8^{\circ}\text{C}$ axillary) from Day 1 through Day 28 postvaccination
- MAAEs, SAEs, deaths, and dengue-related events from Day 1 through Month 12 postvaccination

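### The only fever intensity scale is defined for oral temperature from 38.0°C, but the trial records axillary temperature and counts fever from 37.8°C, with no rule linking the two

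*Combined protocol and SAP*

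**What the plan says.** **Measurement.** Section 8.3.2 says of the vaccination visit: "Vital signs are part of the physical examination at Visit 1 (Day 1) and include axillary body temperature". For the follow-up period it says: "Axillary temperatures will be recorded by participants on the eVRC from Day 1 through Day 28 postvaccination".

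**Fever definition.** The note to Table 2 in Section 8.3.6 reads: "Protocol-specified fever is defined as axillary temperature of ≥37.8°C". The same site and threshold appear in Sections 1.2, 1.3.2, 4.1 and 8.3.2, in the acute febrile illness exclusion of Section 5.2, and in the elevated-temperature endpoint of Section 9.4.2.

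**Duty to grade.** Section 10.3.5 states: "An overall intensity grade will be assigned to injection-site AEs, specific systemic AEs, other systemic AEs, and vital sign (temperature) AEs", and refers to the tables that follow it. Section 8.1.11 has investigators grade AEs collected on the eVRC according to Appendix 3. Section 8.3.6 makes fever seen at an acute visit a reportable AE: "Febrile events evaluated from Day 1 through Day 28 will also be reported as an NSAE".

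**The scale.** The one temperature table, in Section 10.3.5, gives Grade 1 as "38.0 to 38.4 100.4 to 101.1" (°C, then °F). Grade 2 is 38.5 to 38.9°C, Grade 3 is 39.0 to 40.0°C and Grade 4 is above 40.0°C. Its footnote defines the values as "Oral temperature; no recent hot or cold beverages or smoking".

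**The concern.** Two things do not meet. The scale begins 0.2°C above the protocol's own fever threshold, and it is written for a site that the protocol names nowhere else. The documents give no axillary version of the scale, no conversion, and no rule for readings of 37.8 to 37.9°C.

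An investigator can therefore follow every instruction and still be stuck. A participant with two consecutive days at 37.8°C meets the fever definition and attends an acute visit. If that visit falls within Day 1 to Day 28, it generates a nonserious AE that needs a grade, and the temperature table offers none.

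At stake is the reported severity of fever after a live vaccine. Fever is not among the solicited events of Table 4, so under Section 8.4.7.2 a reported fever is an unsolicited AE. Section 9.4.2 summarises unsolicited systemic AEs by maximum intensity, and that is where an ill-defined fever grade would appear.

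**Working it through.** **Inputs**
- Bands: Section 10.3.5, as listed above, stated to 0.1°C and labelled oral.
- Fever threshold: axillary 37.8°C (Sections 8.3.2, 8.3.6 and 9.4.2).
- Axillary-to-oral offset: not in the documents. Assumed here to be 0 to 0.6°C, with axillary reading lower.

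**Step 1: is 38.0°C the intended lower edge?** With F = 1.8 × C + 32:
- 38.0°C gives 100.4°F, 38.4 gives 101.1, 38.9 gives 102.0 and 40.0 gives 104.0. All match the table.
- 38.5°C gives 101.3°F and 39.0°C gives 102.2°F. The table prints 101.2 and 102.1, the next 0.1°F step after the band below.

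The lower edge agrees in both units, so 38.0°C is not a conversion slip.

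**Step 2: map readings as written.** From 37.8°C upward in steps of 0.1°C, only 37.8 and 37.9°C (100.0 and 100.2°F) have no grade. Every reading from 38.0°C has one. This step needs no assumption.

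**Step 3: effect of the measurement site.** Add the assumed offset to each of the 26 readings from 37.8 to 40.3°C and grade again.

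| Assumed offset (°C) | Readings whose grade changes, of 26 | Readings left with no grade |
|---|---|---|
| 0 | 0 | 37.8, 37.9 |
| 0.1 | 4 | 37.8 |
| 0.2 | 8 | none |
| 0.3 | 11 | none |
| 0.5 | 17 | none |
| 0.6 | 18 | none |

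The last row by hand: 37.8 and 37.9 gain a grade (2), 38.0 to 38.4 leave Grade 1 (5), 38.5 to 38.9 leave Grade 2 (5), and 39.5 to 40.0 leave Grade 3 (6). The sum is 2 + 5 + 5 + 6 = 18. These are counts of scale steps, not of expected participants.

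**Step 4: largest shift.** At 0.6°C, axillary 38.4 (Grade 1) becomes 38.4 + 0.6 = 39.0 (Grade 3), which is two grades. At 0.5°C it becomes 38.9 (Grade 2), which is one grade. Among readings that already have a grade, the two-grade shift occurs only at the top of the assumed range.

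**The case against.** The case for leaving this alone is substantial. Both randomized, blinded arms use the same scale, so no bias between arms is shown. Section 9.6.2.1 treats the unadjusted safety intervals as descriptive. The primary and secondary endpoints, the sample size, the yes/no elevated-temperature endpoint and the suspected-dengue trigger do not use the fever grade. All of this stands, and it limits the point to a minor one.

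Three stronger readings are tempting, and the documents do not support them:

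- **Severe fever will be under-reported in both arms.** This needs an axillary-to-oral offset of known sign and size. The documents give none, and the assumed range includes zero.
- **Fever counts by grade are bound not to add up to the elevated-temperature count.** Table 6 plans descriptive statistics and a between-group interval for elevated temperature, with no breakdown by grade. Nor does the protocol say that every eVRC reading of 37.8°C or more is an AE. The two counts were never required to match.
- **Fevers at 37.8 to 37.9°C go wholly ungraded.** They have no grade on the temperature scale. An investigator could grade a febrile illness on the Other Systemic AE scale, which rests on interference with activity. No text directs this for temperature, and doing so would mix two scales that are not equivalent. The data entry guidelines, which might help, are not part of the documents.

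The mismatch itself remains. The intensity rule is explicit, and it cannot be applied to the trial's own lowest fever readings.

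**Conclusion.** The point holds as an internal inconsistency of minor severity. It is certain from the text that axillary readings of 37.8 and 37.9°C count as fever and have no grade on the temperature scale. It is equally certain that all other axillary readings would be placed in bands defined for oral temperature without a conversion rule.

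The size and direction of any misgrading are not established. Under the assumed offset of 0 to 0.6°C the shift runs from none to two grades, and that range rests wholly on the assumption. The consequence is limited to summaries of fever intensity. Which threshold or measurement site is right is not a question that the documents settle.

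**What to change.** Reconcile the temperature table in Section 10.3.5 with Sections 8.3.2, 8.3.6 and 9.4.2. The scale should state the route to which its bands apply and cover every reading that meets the protocol's own fever definition. The sponsor sets the cut-offs.

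In addition, tabulate maximum axillary temperature from Day 1 through Day 28 by arm, in fixed bands starting at the protocol's stated threshold. This shows fever severity directly, without depending on the grade.

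The cost is small: an appendix edit, a change to any grading program, and one table. The eVRC temperatures are already collected, so no new data are needed. Under the opening of Section 9, the added table can be documented in the sSAP if the data are still blinded; otherwise it should be clearly identified in the CSR as post hoc. The downside is that the bands may differ slightly from the source scale. Section 10.3.5 already describes its scales as adapted from that source.
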